#### BACKGROUND:

The goal of the proposed project is the development and evaluation of a novel mobile medical application for the detection and monitoring of strabismus (eye misalignment). The image analysis technology necessary to measure strabismus using the corneal reflection technique (Photographic Hirschberg Test) has been available for many decades (Brodie 1987), however it has never been deployed using a smart phone. A smart phone platform will eliminate barriers of cost (since the hardware is maintained and updated by the smart phone industry), leading to rapid widespread application and allowing the technology to finally reach its potential level of impact for children's' eve care in the detection and management of strabismus. Strabismus causes visual confusion and double vision which ultimately results in the brain suppressing vision from the deviated eye. In children this results in under-development (amblyopia) with permanent vision loss in the deviated eye if not detected and treated at a young age (Rowe, 2012). Strabismus in children is also associated with coordination problems such as postural instability (Lions et. al. 2013) and severe social disadvantages (Lukman et. al. 2011). Strabismus develops in an estimated 3-8% of children in the U.S. (Taylor et.al. 2011; Cotter et.al. 2009; Rowe 2012). The prototype smart phone app (Referred to here as the Mobile Eye Alignment App – MEAA), uses photographic analysis of the corneal reflection (Purkinjie image) generated by the smart phone camera flash. The corneal reflection method uses the displacement of the reflection from the center of the pupil in the deviated eye to calculate the amount of eye misalignment.

This measurement technique will be deployed for the proposed project using the hardware of the Samsung Galaxy, a popular phone with an Android operating system. Preliminary results suggest the app can measure differences in eye alignment of  $1.6^{\circ}$  (2.8 prism diopters). If successfully developed, the app has potential to be utilized to advance pediatric strabismus research by facilitating and reducing the cost of collecting enormous amounts of data from the general population and underserved or remote populations for epidemiologic studies and allowing researchers to capture eye alignment data much more frequently than is currently possible. Such a tool could better delineate the natural history of strabismus and perhaps help determine its causes.

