## AIM 2:

Evaluate the strabismus app accuracy and feasibility in a clinical environment. Participants with strabismus will be tested with both the app and clinical methods and analyzed for levels of agreement and test-retest repeatability, satisfaction with the app evaluation, impact on symptoms, and perceived value.

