## **HYPOTHESES**:

For strabismus ranging from 1 to 30 prism diopters (target range), the optimized version of the app will provide measurements which are not significantly different from the ground truth (simulated strabismus) or clinical tests of eye alignment.

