## Secondary outcome:

1) Accuracy of the app quantified by calculating the mean difference between the app and simulated or measured strabismus.

2) Test-retest repeatability

3) Robustness measure: calculation of the percentage of capture failures (capture failures/ total number of attempted image captures)

4) Analysis of the effect of different factors (i.e. age, iris color, refractive error) on the accuracy.

5) Success rate of tele-strabismus consult and perceived value (captured in a perceived value survey).

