Figure 2. Cover testing mode for dissociated measurements using the app. (Top row) Alternating cover–uncover test using the video-based cover test mode. This novel operational mode can be used for dissociated measurements. The examiner alternately covers the eyes (first two images on top row). The frame with both eyes uncovered (third image on the top row) is selected for automatic processing by the app for measurement of the eye deviation. (Bottom row) Eye movement trace after offline processing of the video of the alternate cover test shows the movements of the eyes after the cover is removed. Negative values show temporal deviation (outward), whereas positive values show nasal deviation (inward). There is a brief duration after removing the cover during which the deviation can be measured (highlighted by the oval gray zone). It should be noted that the eye movement trace in this figure was generated by processing the video recorded by the smartphone on a desktop computer using the same image processing software used in the app, but may be included as part of the app in the future. Permission to publish photograph was obtained via a signed consent to publish document.

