Statistical Analysis Plan

Produced during publication of data

[name], [name], [name], [name], [name]; Development and Preliminary Evaluation of a Smartphone App for Measuring Eye Alignment. *Trans. Vis. Sci. Tech.* 2019;8(1):19.

August 1, 2019

Aim 1: Simulated Strabismus

The Hirschberg ratio (HR) for each subject was determined using data from all 13 fixation points by plotting the app measurement against the known angular deviation for each fixation point, and determining best fit of this scatter plot using linear regression. The slope of this function represents the individual's HR and the *y*-intercept is the individual's angle κ (the angle between the visual and optical axes, represented as κ).^{18,19} We measured the within-subject test–retest repeatability of the app in estimating the HR and κ using a Bland-Altman²⁰ plot to compute 95% confidence interval (CI) of the difference between two trials. Furthermore, we tested the accuracy of using a population average value of the HR by comparing the absolute gaze angles estimated by the app measurements and the true deviation of the fixation targets (via regression analysis using MATLAB; Mathworks, Natick, MA). The HR used for a subject was the average HR of the rest of the subjects.

Aim 2: Strabismus

Linear regression analysis was used to compare the app measurements of strabismus angle with cover test with prism neutralization CTPN measurements. Since the CTPN measurements were done at near fixation to facilitate direct comparison with the app measurements, corrections were made to the recorded CTPN values during data processing to account for the finite distance between the prism and center of rotation of the eye.²² We arrived at a value of the distance between prism and center of rotation of eye by assuming a population average value of 24 mm for axial length²³ and a back vertex distance of 10 mm.

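### The Aim 2 regression does not say how inward and outward deviations are handled; if signed values share one line, slope and R-squared can overstate how well the app grades size

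*SAP*

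**What the plan says.** The SAP's Aim 2 paragraph specifies the comparison in one sentence: "Linear regression analysis was used to compare the app measurements of strabismus angle with cover test with prism neutralization CTPN measurements". The rest of the paragraph concerns a prism-distance correction to the CTPN values. It gives no sign rule, direction term, separate fit, criterion for slope or intercept, or count of inward and outward cases.

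The Protocol promises more. Under Aim 2: "Participants with strabismus will be tested with both the app and clinical methods and analyzed for levels of agreement and test-retest repeatability". Under Secondary outcome: "Accuracy of the app quantified by calculating the mean difference between the app and simulated or measured strabismus", without saying whether that difference is signed. The SAP's only Bland-Altman analysis belongs to Aim 1: "We measured the within-subject test–retest repeatability of the app in estimating the HR and κ using a Bland-Altman". It addresses repeatability of the Hirschberg ratio (HR) and angle kappa, not app against CTPN.

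On direction, the Protocol's clinical eligibility asks for strabismus without restricting it. The Hypotheses section gives the target range as 1 to 30 PD, a size with no sign. The one sign convention (outward negative, inward positive) is in the Figure 2 legend under Study Procedures and describes an eye-movement trace, not the Aim 2 regression.

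**The concern.** The clinical question is whether the app measures how large a deviation is. On one signed axis, inward cases lie above zero and outward cases below it, so much of the variance in CTPN is the distance between the two group means. An app that gets the direction right captures that part whether or not it grades size well. The pooled slope and R-squared then mix two abilities, telling inward from outward and measuring size, and the first can carry the second.

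What is at stake is a compressed or saturating scale that passes as good agreement. The mean difference does not guard against this: in a balanced signed sample, errors that shrink readings towards zero have opposite signs in the two directions and cancel.

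**Working it through.** The documents give no Aim 2 slope, R-squared, sample size or inward/outward split, so there is no planned figure to reproduce. The check is of the mechanism, with assumptions marked.

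**Inputs**
- Size m from 1 to 30 PD (Protocol, Hypotheses). The uniform shape is assumed.
- Noise SD 2.8 PD. The Protocol Background gives "2.8 prism diopters" as a difference the app can measure; using it as a noise SD is an assumption.
- Inward share p: not in the documents, so 50%, 70%, 90% and 100% are shown.
- Moments: E[m] = 15.5; Var(m) = 29²/12 = 70.08; E[m²] = (30³ − 1)/(3 × 29) = 310.33.

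**1. Compressed app, within one direction.** Reading = 6 + 0.6m + noise. Slope = 0.60. R-squared = 0.36 × 70.08 / (0.36 × 70.08 + 2.8²) = 25.23/33.07 = 0.76.

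**2. The same app, signed and pooled.** Let s = ±1 be direction, x = sm, y = s(6 + 0.6m) + noise, and q = 2p − 1.
- Var(x) = 310.33 − 240.25q²
- Cov(x,y) = 0.6 Var(x) + 6 × 15.5 × (1 − q²)
- Var(y) = 0.36 Var(x) + (36 + 2 × 6 × 0.6 × 15.5)(1 − q²) + 7.84

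| Inward/outward | Var(x) | Cov | Var(y) | Slope | R-squared |
|---|---|---|---|---|---|
| 50/50 | 310.33 | 279.20 | 267.16 | 0.90 | 0.94 |
| 70/30 | 271.89 | 241.26 | 229.71 | 0.89 | 0.93 |
| 90/10 | 156.57 | 127.42 | 117.34 | 0.81 | 0.88 |
| 100/0 | 70.08 | 42.05 | 33.07 | 0.60 | 0.76 |

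**3. An app with no jump at zero.** Suppose it reads correctly up to 20 PD and stays at 20 beyond, with the same noise. Call the noise-free reading r.
- E[r] = (199.5 + 200)/29 = 13.78
- E[mr] = (2666.33 + 5000)/29 = 264.36
- E[r²] = (2666.33 + 4000)/29 = 229.87
- Within direction: covariance = 264.36 − 15.5 × 13.78 = 50.83; slope = 50.83/70.08 = 0.73; R-squared = 50.83²/(70.08 × 47.94) = 0.77.
- Pooled at 50/50: slope = 264.36/310.33 = 0.85; R-squared = 264.36²/(310.33 × 237.71) = 0.95.

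**4. Purely proportional error (reading = 0.6 × true).** The slope is 0.60 within direction and pooled, so the line reports it correctly. R-squared still rises, from 0.76 to 0.36 × 310.33/(0.36 × 310.33 + 7.84) = 0.93 at 50/50.

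**5. Would the mean difference help?** For the app in step 1 the average error in size is 6 + 0.6 × 15.5 − 15.5 = −0.2 PD, and the signed mean at 50/50 is 0. The SD of differences at 50/50 is √(0.2² + 0.16 × 70.08 + 7.84) = 4.37 PD, so 95% limits of agreement are about ±8.6 PD. The limits reveal what the mean difference and R-squared do not.

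**6. Unsigned values with a constant 3 PD nasal offset, noise SD 1.4 PD (both assumed).** Orient each difference by its CTPN direction. Mean = 3(2p − 1): 0 at 50/50 and 1.2 PD at 70/30. SD = √(9(1 − q²) + 1.4²): √10.96 = 3.3 PD and √9.52 = 3.1 PD, against 1.4 PD without the offset. Taking absolute values of the readings instead gives means of about 0.1 and 1.3 PD and SDs of about 3.2 and 3.0 PD. With signed values the offset would appear in the intercept and the mean.

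**The case against.** The strongest reply is that the SAP never says inward and outward cases share one signed line. That stands. A reader might infer it from an unstratified regression in an unrestricted strabismus population, and it is the natural reading, but sign handling and case mix are simply not stated.

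A second tempting inference is that the regression misleads however sign is handled. The documents and the arithmetic do not support that. Take an app that knows only direction and always returns 15.5 PD. Signed and pooled at 50/50, it gets slope and (without noise) R-squared of 240.25/310.33 = 0.77; unsigned, it gets 0 for both and is exposed. The offset problem in step 6 is a separate matter, and it leaves a visible mark in the SD.

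Third, the Protocol describes converting corneal-reflection displacement with an HR, which is a continuous scaling. A wrong HR gives proportional error, which the pooled slope shows correctly. The app in step 1 needs a 12 PD jump at zero (−6 to +6) and the direction-only app a 31 PD jump; nothing in the documents suggests either. This is fair against those examples, but step 3 has no jump and still moves the slope from 0.73 to 0.85.

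Fourth, Aim 1 tests grading against 13 known targets over about ±23 PD. That makes a direction-only app implausible, but those subjects have no strabismus and the range stops short of 30 PD. It does not replace the comparison in patients.

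Finally, the effect weakens as the split becomes unequal. It does, though slowly: at 90/10 the slope is still 0.81 against 0.60.

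**Conclusion.** The point holds conditionally. The plan leaves direction unspecified in its only Aim 2 comparison, and no app-versus-CTPN agreement analysis backs it up. If signed values are pooled, R-squared is raised whenever both directions are present, and the slope is raised when the app compresses or levels off at larger angles. In the illustrations, within-direction slopes of 0.60 and 0.73 become 0.90 and 0.85 at an even split, with pooled R-squared of 0.94 and 0.95. If values are unsigned, the risk is a different one: a constant offset reported as scatter.

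The sizes rest on assumed uniform magnitudes, noise of 2.8 PD (1.4 PD in step 6), an assumed split, and hypothetical error patterns. The documents do not show that the app has these errors, and they do not establish that the reported regression was distorted. The plan simply could not tell. This is a cheap improvement to the analysis, not a fault that invalidates the study.

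**What to change.** In the SAP's Aim 2 paragraph:
- State that signed values are used, and give the number of inward and outward cases.
- Report slope, intercept and residual SD of app on CTPN for each direction, descriptively if one direction has few cases.
- Report the app-minus-CTPN mean difference and 95% limits of agreement, overall and by direction. This also supplies the agreement analysis promised under Aim 2.
- Do not cite the pooled slope or R-squared alone as evidence of agreement.

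This takes a few sentences and a re-analysis of data already collected. The cost is precision: each within-direction estimate rests on fewer patients, so its interval is wider, and its R-squared will usually look lower than the pooled one.
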